COVER PAGE

NCT06079853

Date of Protocol Approval: 10/18/2023

Study Title: The Use of Physiologic Measures and Sleep Health Promotion to Identify and Mitigate Predisposing Factors of Suicidal Ideation in Nurses

PI: [name], RN, ANP-BC, FAAN

PI Contact: [contact]

Sponsor: Columbia University School of Nursing

STUDY PROTOCOL

The purpose of this study is to generate longitudinal pilot data that investigates 1) which factors (stressful life events, psychiatric characteristics, and work environment characteristics) are associated with stress and subsequent suicidal ideation; and 2) to explore the preliminary impact of an existing evidence-based sleep intervention, *Somni*^{®14}, on stress, psychological health, and suicidal ideation in working nursing professionals. The specific aims are:

Aim 1. To investigate associations between sleep, stressful life events (life stressors, discrimination, lateral violence), psychiatric characteristics (psychiatric diagnosis, subjective mood), work environment characteristics (workload, shift type and duration, overtime, nurse work environment, and team relations) and stress (self-reported and heart rate variability) in working nursing professionals while controlling for standard covariates known to influence stress. *Hypothesis 1:* Suboptimal work environment characteristics are positively associated with self-report and physiologic indicators of stress [heart rate variability (HRV)]. *Hypothesis 2:* Poor sleep (duration and quality) will be positively associated with self-report and physiologic indicators of stress (HRV).

Aim 2. To determine if stress exposure (self-report and HRV) are associated with predisposing factors (sleep, stressful life events, additional psychiatric characteristics, and work environment characteristics), and to explore whether stress mediates the effect of predisposing factors on suicidal ideation in working nursing professionals. *Hypothesis:* Nurses with low HRV are at higher risk for suicidal behavior when exposed to poor sleep, the presence of psychiatric characteristics (e.g. Depression), stressful life events, or suboptimal work environment characteristics (e.g., poor team relations).

Exploratory Aim. To explore the preliminary impact of an existing sleep intervention (*Somni*[®]) on self-reported stress, HRV, sleep, and psychiatric health outcomes including depression, burnout, and suicidal ideation.

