4. Sleep Intervention (Weeks 4-8) *Somni*[®] is an evidence-based personalized sleep intervention aimed at promoting optimal sleep health and has demonstrated effectiveness in shift workers outside the healthcare sector (e.g. Disney). *Somni*[®] consists of a sleep kit and a smart phone application. The sleep kit is box of items with demonstrated past evidence of improving sleep health: Blue light blocking glasses, white noise machine, lavender spray, ear plugs, light blocking eye mask, and herbal tea. Rather than dictate a “one size fits all” approach to optimize sleep health, there is current evidence that individualized sleep interventions are recommended to optimize sleep quality. *Somni*[®] permits individualized sleep quality promotion and participants are able to select their preferred use, timing, and duration of each of the box contents. The kit is accompanied by a *Somni*[®] smartphone app that prompts participants to input the use of each component in the kit and provide a subjective sleep quality rating each day. Drs. [name] and [name] have partnered with the developers of *Somni*[®] who will provide free sleep kits and app access to our study participants. The *Somni*[®] app is interoperable with the *Oura Ring*[®] and will automatically sync all physiologic and sleep data together in one location, fully accessible to the participants, and displayed in graphs in the *Somni*[®] app that are easy to read and interpret (e.g. total daily steps; daily sleep hours). *Somni*[®] will be implemented Weeks 4 through 8 to investigate its preliminary impact on stress and suicidal ideation by comparing survey and physiologic metrics from Weeks 1-4.

STATISTICAL ANALYSIS

First, we will calculate composite scores of individual measures (sleep, stressful life events, psychiatric characteristics, and work environment characteristics). Descriptive statistics will be calculated including means

and standard deviations (normally distributed values), median and interquartile range (non- normally distributed variables), or absolute and relative frequencies (categorical variables). Outliers and missing data will be assessed (outliers > 3 standard deviations from the mean will be removed). Significance level will be set at $\alpha = 0.05$.

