Aim 2. We will classify nurses into quartiles of high (top 25%), medium (middle 50%), and low (bottom 25%) HRV. We will use descriptive statistics to examine individual measures and composite scores of factors (sleep, stressful life events, psychiatric characteristics, work environment characteristics) and suicidal behavior [C-SSRS score]. To evaluate the change in suicidal ideation over time and the impact of each factor composite score, we will fit conditional latent growth curve models using 3 data points. The models will be expressed such that, given mean HRV and baseline composite scores for each factor category: $y_{it} = (\mu_a + \mu_\beta \lambda_t + \gamma_1 HCC_i + \gamma_2 WEC_i) + (\zeta_{ai} + \zeta_{\beta i} \lambda_t) + \varepsilon_{it}$ where y_{it} is the C-SSRS score for nurse i at time t , μ_a is the latent variable for the intercept value (baseline score), μ_β is the random latent variable for slope (growth over time) for nurse i multiplied by the vector of factor loadings specifying time, λ_{it} , ε_{it} is the time-specific residual for nurse i , ζ_{ai} and $\zeta_{\beta i} \lambda_t$ are random components of the latent intercept and slope variables, respectively. Sleep, stressful life events and psychiatric characteristics are fixed (time-invariant) predictors. The factor loadings for time on slope can be fixed to adjust for gaps in outcomes, which would allow for modeling more distant (e.g., 2025) data from baseline without increasing the number of timepoints included in the model. Further, we anticipate fluctuations in HRV over time. To accommodate the change in trend, we will explore both linear and quadratic growth functions. Baseline global sleep scores (PSQI), stressful life events, psychiatric and work environment characteristics will serve as predictors of suicidal ideation change over time. Individual nurse characteristics and psychiatric characteristic controls will be included as an interaction term to compare curves across nurses. To explore whether stress mediates the effect of predisposing factors on suicidal ideation, we will compare the models assessing the effect of predisposing factors on suicidal ideation with and without the mediator outlined by Barron and Kenny difference method which be used to gauge the size of the mediation effect.

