Aim 3. We will calculate descriptive statistics, percentages, and frequencies for 1) each *Somni*[®] sleep kit component 2) subjective sleep quality via *Somni*[®] app 3) global sleep scores (PSQI score) and HRV. We will test differences in global sleep scores (PSQI), mean sleep duration (Oura ring), mean subjective sleep quality and use of sleep kit components at the individual level between the 3 data points. We will report the effect sizes and will test for significance in the model for each psychosocial and work environment factor, each *Somni*[®] sleep kit component (mean weekly frequency), and the mean PSQI score while controlling for age, sex, gender, race, and history of psychiatric diagnosis. We will repeat the same analysis modeling mean C-SSRS as the dependent variable. To evaluate the change in suicidal behavior over time and the impact of global sleep (PSQI score) and each *Somni*[®] sleep kit component (mean weekly frequency), we will fit conditional latent growth curve models.

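### The 3-SD outlier removal exempts no variable, so it reaches C-SSRS. If most nurses score 0, it can remove only genuine high scores, and C-SSRS should be exempt.

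*Combined protocol and SAP*

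**What the plan says.** The outlier rule stands in the general opening of STATISTICAL ANALYSIS, before any aim: "outliers > 3 standard deviations from the mean will be removed". It names no variable and no exception. It does not ask for a check that the value is an error, and it offers no sensitivity analysis with the values kept. It also leaves open whether the single value or the whole nurse is dropped, and whether the mean and SD are taken within each survey or over all three.

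C-SSRS then enters as a numeric outcome:

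- **Aim 2.** The modelled quantity "is the C-SSRS score for nurse i at time t", and "we will fit conditional latent growth curve models using 3 data points".
- **Aim 3.** After the sleep analysis, "We will repeat the same analysis modeling mean C-SSRS as the dependent variable", followed by growth curves for suicidal behavior.

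Ideation is a named target of the study. The Exploratory Aim lists "psychiatric health outcomes including depression, burnout, and suicidal ideation", and component 4 of STUDY DESIGN says Somni is introduced "to investigate its preliminary impact on stress and suicidal ideation by comparing survey and physiologic metrics from Weeks 1-4". Two other provisions do not limit the rule. The median and interquartile range for non-normal variables concern descriptive summaries, and the count distributions under Aim 1 are tied to the stress outcome.

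**The concern.** A 3-SD rule suits a roughly symmetric measure in which an extreme value may well be a recording error. An ideation score in working nurses may have a floor at 0 and be mostly zeros. A severe score is then far from the mean because ideation is rare, not because the entry is wrong. Removal would depend on the outcome itself and would take out the nurses the study sets out to understand.

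Two things are at stake. The level of ideation would be understated in a pilot meant to inform a larger study. The change over the Somni period could also be misstated, because a nurse who worsens sharply is the one most likely to be dropped.

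**Working it through.** The plan gives no C-SSRS figure to reproduce: no sample size, scoring range, prevalence or SD. From the documents come the 3-SD rule, the three surveys (baseline, Week 4, Week 8) and the use of C-SSRS as a score. Assumed here: a 0-5 score, and among nurses with ideation 45/25/15/10/5% scoring 1/2/3/4/5 (skewed), or 20% at each score (even). SD uses n-1.

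**1. Direction.** If more than half the nurses score 0, the median is 0. A mean never lies more than one SD from its median, so 0 is at most one SD below the mean and cannot be flagged. Only high scores can be removed.

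**2. When the rule bites.** If k of n nurses share one non-zero score and the rest score 0, with p = k/n, each scorer has z = sqrt[((1-p)/p) x ((n-1)/n)].

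- n=50, k=4: sqrt(11.5 x 0.98) = 3.36, so all four are removed.
- n=50, k=5: sqrt(9 x 0.98) = 2.97, so none is removed.
- All such scorers are removed up to 1 of 20, 2 of 30, 4 of 50 and 9 of 100.
- The largest z any value can reach is (n-1)/sqrt(n), which is 2.85 at n=10 and 3.02 at n=11. Below 11 nurses nothing can be removed.

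**3. One mixed example.** Take n=50 with 45 zeros and scores 1, 1, 2, 4, 5. Mean 0.260, SD 0.944, cut-off 0.260 + 3 x 0.944 = 3.09. The 4 and the 5 go, and the mean becomes 4/48 = 0.083.

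**4. Average loss at one survey** (simulation, 20,000 data sets per cell, n=50; loss = 1 - after/before, for example 1 - 0.097/0.206 = 53%):

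| With ideation | Mean before (skewed) | Mean after | Loss | Scores 4-5 removed | Loss, even mix |
|---|---|---|---|---|---|
| 5% | 0.102 | 0.029 | 72% | 100% | 77% |
| 10% | 0.206 | 0.097 | 53% | 96% | 54% |
| 20% | 0.409 | 0.292 | 29% | 76% | 18% |
| 30% | 0.614 | 0.524 | 15% | 46% | 3% |

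At 10% with ideation (skewed mix), the mean goes from 0.205 to 0.101 at n=30 and from 0.205 to 0.093 at n=100.

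**5. A change from Week 4 to Week 8.** Take n=50, with eight nurses at 1 in both surveys and two going from 0 to 4.

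- Week 4: mean 0.16, SD 0.37, z of a score of 1 = 2.27. Nothing is removed.
- Week 8: mean 16/50 = 0.32, SD 0.84, z of a 4 = 4.36. Both are removed.
- Mean change with all data: 8/50 = +0.16 (95% CI -0.07 to 0.39). After removal, over 48 nurses: 0.00.
- The same pattern with n=20 and three nurses at 1 gives z of 2.79 for the 4s (2.92 if those three fall to 0), so nothing is removed.

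**6. Bias in a slope.** Differences between rows of the table in step 4 show what a per-survey rule does to a rise in prevalence. From 5% to 10% the true rise of 0.206 - 0.102 = 0.104 becomes 0.097 - 0.029 = 0.068. From 20% to 30% the true rise of 0.614 - 0.409 = 0.205 becomes 0.524 - 0.292 = 0.232, which is larger. A linear growth-curve simulation (random intercept and slope, removed values treated as missing, n=50, 200 data sets per setting, Monte Carlo SE 0.002 to 0.016) is indicative only. It gives these slopes over 8 weeks:

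| Scenario | No rule | Per survey | Pooled |
|---|---|---|---|
| 10% with ideation, two more nurses go 0 to 4 | 0.164 | 0.094 | 0.008 |
| Ideation spreads from 10% to 16% | 0.128 | 0.116 | 0.071 |
| Ideation spreads from 20% to 30% | 0.216 | 0.237 | 0.166 |

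**7. Low HRV, illustrative only.** With ideation in 20% of a low-HRV quarter and 5% of the rest (n=50, skewed), the mean difference falls from 0.309 to 0.134, a loss of 1 - 0.134/0.309 = 57%. At 30% against 10% it falls from 0.406 to 0.256 (37%).

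**The case against.** The strongest reply is that every size above is assumed. That stands: the plan gives none of the inputs, and the rule often does little. With a slightly different severity mix (40/30/15/10/5%) and 40% of nurses scoring above 0, at least one removal occurs in only 49% of simulated samples at n=50 and 31% at n=30. A sensible analyst might also leave C-SSRS alone, but the text does not say so.

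Several stronger readings are tempting, and the documents do not support them.

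- **The rule hides a significant harm.** A reader might infer this from step 5. Even with all data kept, the change of +0.16 is not significant (p=0.16). What moves is the estimate.
- **The rule turns harm into significant benefit.** If four of the eight other nurses improved, a paired t-test after removal would give p=0.04, but an exact sign test on the same data gives p=0.125. The plan names neither test for C-SSRS, so no significance threshold can be attached to it.
- **The slope is always pulled down.** Step 6 shows that a per-survey rule does little, or pushes the slope slightly up, when worsening is spread over many nurses. The largest losses need the pooled reading or a few large jumps. The simulation is linear only, while Aim 2 will also explore quadratic growth.
- **Aim 2 loses 57% of its effect.** The hypothesis is that "Nurses with low HRV are at higher risk for suicidal behavior when exposed to poor sleep", but the plan attaches only descriptive statistics to the HRV groups. A low-quarter-against-rest difference is not a stated estimate.
- **Omitting a count of worsened nurses is an analysis error.** No such count is stated, but the repeated analysis in Aim 3 may include a comparison over the three time points, and the data allow a cross-tabulation. A shift table is an added output, not a correction.

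**Conclusion.** The point holds in a limited form. That the rule reaches C-SSRS follows from the text. That it can remove only high scores follows once more than half the nurses score 0. Its size is conditional: at n=50 on a 0-5 score, the mean is understated by about 53% (skewed mix) or 54% (even mix) at 10% with ideation, and by about 29% or 18% at 20%. The loss is smaller at 30% and nil in the n=20 example. For change over time, the plan leaves the size and direction of bias undetermined because it does not say whether the rule works per survey or pooled. The case for changing the plan does not need any one of these figures. The removal has no justification for this outcome, and its effect depends on quantities the plan leaves open.

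**What to change.** Add one sentence to the opening paragraph of STATISTICAL ANALYSIS: the 3-SD removal does not apply to C-SSRS in any descriptive, Aim 2 or Aim 3 analysis, and a C-SSRS value is changed only when a data-entry error has been verified.

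The cost is SAP wording only, with no new data. The downside is that extreme scores will have more influence on the mean-based models. The exemption does not by itself make those models well suited to a score with many zeros.

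Optional: a descriptive within-nurse shift table of C-SSRS from Week 4 to Week 8, with baseline to Week 4 as the pre-Somni reference and no causal attribution to Somni. It uses the three surveys already planned. Exact intervals on the counts would be wide: 2 of 50 is 4.0%, with a 95% interval of 0.5% to 13.7%.

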Aim 1. We will calculate bivariate Pearson or Spearman's rank order correlation coefficients as well as simple linear regression and univariate ANOVAs. We will use linear mixed models to examine the relationships between individual and composite scores of factors (sleep, stressful life events; psychiatric characteristics; work environment characteristics) and 1) self-report stress and 2) HRV, while controlling for personal characteristics (age, sex, highest degree earned, years of experience, years of practice in current environment, smoking status). We propose the following model to test all hypotheses:

$Y_g[E(i)] = \beta_0 + \beta_1 X_i + \beta_2 F$ where Y_g represents the outcomes measure (self-report and HRV separately) for each participant i . X_i are the individual-level covariates (e.g., sex, gender, race, age, mental health history), F represents each job stressor and work environment variable. As the primary outcome is stress (mean score and mean HRV), possible distributions such as Poisson, zero-truncated Poisson, negative binomial, or zero-truncated negative binomial will be assessed to determine the best fit link function.

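### Aim 1 describes its adjusted model in two ways that disagree: the equation meant for every hypothesis names no sleep term, shows no participant or time structure, and shares only age and sex with the covariates listed before it

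*Combined protocol and SAP*

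**What the plan says.** All of this is in Statistical Analysis, Aim 1, of the combined protocol and SAP, unless another place is named.

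- **Prose model.** The stated intention is to "use linear mixed models to examine the relationships between individual and composite scores of factors (sleep, stressful life events; psychiatric characteristics; work environment characteristics"; the outcomes are the two stress measures, self-report and HRV. Adjustment is described as "controlling for personal characteristics (age, sex, highest degree earned, years of experience, years of practice in current environment, smoking status". That covariate list has six items and is closed.
- **Equation.** The next sentence reads "We propose the following model to test all hypotheses". The right-hand side has three terms: an intercept, covariates X and a factor F. The definitions that follow say "F represents each job stressor and work environment variable", and X is the "individual-level covariates (e.g., sex, gender, race, age, mental health history". That list has five items and is open.
- **Outcome and distribution.** "As the primary outcome is stress (mean score and mean HRV" introduces the last sentence, which goes on: "possible distributions such as Poisson, zero-truncated Poisson, negative binomial, or zero-truncated negative binomial will be assessed to determine the best fit link function".
- **Hypothesis 2 of Aim 1** (Study Protocol, aims) is about sleep: poor sleep duration and quality are expected to go with self-reported and physiologic stress.
- **Data structure** (Study Design, items 1, 3 and 4). Surveys are given at baseline, Week 4 and Week 8. The ring collects data in Weeks 1-8. Somni runs in Weeks 4-8.
- **Aim 2** adds that "we anticipate fluctuations in HRV over time". Its own equation carries participant and time subscripts and random components.

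**The concern.** A plan may summarise a model in prose and then in symbols, but the two should describe the same model. Here they do not, and the equation is the version assigned to every hypothesis. An analyst who follows the prose includes sleep, adjusts for degree, experience and smoking, and fits a mixed model. An analyst who follows the equation has no named sleep term, adjusts for gender, race and mental health history, and sees nothing that makes the model mixed. It is also unclear whether the outcome is one mean per nurse or one value per survey.

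The choice affects what the plan calls its primary outcome, and nothing prevents it from being made after the data are seen. The time structure matters most for Hypothesis 2. Somni targets sleep and may also change stress. If both move together at Week 8 and the model has no wave term, a shift over time can look like an association between sleep and stress. The pilot's stated purpose is to inform a fully powered study, so such a result could be carried forward.

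**Working it through.** The plan gives no power or effect-size figure for Aim 1, so there is nothing to reproduce. The check is a comparison of the two descriptions, followed by illustrations with assumed inputs.

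**1. Factor domains**

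| Domain | Prose model | Equation |
|---|---|---|
| Sleep | named | in neither F nor X |
| Stressful life events | named | in part at most: lateral violence can count as a job stressor, but non-work events have no named place |
| Psychiatric characteristics | named | only as the covariate mental health history |
| Work environment | named | named |

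One of the two Aim 1 hypotheses has no named term in the equation.

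**2. Model structure.** The prose says mixed. The equation writes no random effect, residual or time index, and the accompanying text defines only the outcome, X and F. Symbols lost in PDF extraction are therefore an unlikely explanation.

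**3. Covariates.** Six in the first list, five in the second, age and sex in both: 6 + 5 − 2 = 9 distinct items, of which 2 are shared. Only in the first: highest degree, years of experience, years in current environment, smoking. Only in the second: gender, race, mental health history.

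**4. Distribution.** All four named families are for counts. The outcomes are a mean score and a mean HRV, in a model called linear.

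**5. Illustration: three rows per nurse, no participant effect.** Assumed: the outcome's intraclass correlation (ICCy), the factor's (ICCx) and a two-sided 0.05 test (the plan gives 0.05 without stating sidedness). Design effect = 1 + 2 × ICCy × ICCx. Actual type I error = 2 × [1 − Φ(1.96/√design effect)].

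| ICCy | ICCx = 1 (factor fixed over time): design effect, error | ICCx = 0.7: design effect, error |
|---|---|---|
| 0.4 | 1.80, 14.4% | 1.56, 11.7% |
| 0.6 | 2.20, 18.6% | 1.84, 14.9% |
| 0.8 | 2.60, 22.4% | 2.12, 17.8% |

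In simulation (2,000 runs per setting, n = 50, 100, 200), a random intercept gave 4.4-5.9% and one mean per nurse gave 4.3-5.9%.

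**6. Illustration: random intercept, no wave term.** Assumed: sleep measured at each survey and entered as a repeated predictor; poor-sleep score and stress both shifted by d SD at Week 8; no association within waves; 2,000 runs per setting. False-positive rates:

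| ICC | n | d = 0.2 | d = 0.3 | d = 0.5 |
|---|---|---|---|---|
| 0.5 | 50 | 5.4% | 9.0% | 20.6% |
| 0.5 | 100 | 5.6% | 11.0% | 39.7% |
| 0.5 | 200 | 7.2% | 15.2% | 65.2% |
| 0.7 | 50 | 6.8% | 12.2% | 44.8% |
| 0.7 | 100 | 7.2% | 17.7% | 71.6% |
| 0.7 | 200 | 11.6% | 32.8% | 94.7% |

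A repeat at n = 100 gave 6/10/39% (ICC 0.5) and 9/18/74% (ICC 0.7).

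**7. The same shift under other readings.** Adding a wave term: 4.6-6.0%. One mean per nurse: 4.5-6.8%. Factor fixed at baseline, stress falling 0.2-0.5 SD at Week 8, random intercept and no wave term: 4.7-6.4%. None of these shows material inflation.

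**The case against.** The strongest reply is that the intent can be recovered. The prose already says linear mixed models, which supplies a participant effect. It lists sleep among the factors, so F can be read as shorthand for all of them. The second covariate list is only a set of examples and may contain the first. The outcome is defined per participant as a mean, which fits one row per nurse.

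Much of this stands, and it limits what can be claimed:

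- A reader might infer that Hypothesis 2 goes untested. The documents do not support that: the unadjusted correlations and regressions can include sleep, and the prose names it. What is missing is a sleep term in the one equation said to test every hypothesis.
- A reader might infer that the planned analysis has a 12-22% error rate. That requires an analyst to set aside the mixed-model sentence.
- A reader might treat the table in step 6 as the expected error. It requires sleep as a repeated predictor. The Aim 2 text treats sleep, stressful life events and psychiatric characteristics as fixed over time, and the Aim 1 text is silent. The largest values also need a 0.5 SD shift in both variables, a figure the documents do not give.
- Highest degree and years in current environment are not in Table 1's demographics row. That does not show they go uncollected, because the surveys are also said to cover personal characteristics.
- The distribution list is open and fit will be assessed, so that part is secondary.

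The reply does not remove the conflict. The plan does not say that the prose overrides the equation. The closed list still omits gender, race and mental health history. If the outcome is one mean per nurse, nothing shown makes the model mixed, and a Weeks 1-8 HRV mean blends time before and during Somni.

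**Conclusion.** The point holds as an internal contradiction in the Aim 1 analysis text and should be corrected before data are seen. The conflicts over sleep, participant and time structure, and covariates rest on the text alone. The size of the statistical consequence cannot be determined, because the documents give no sample size, ICC or expected shift. Under some permissible readings it is negligible; under others a shift over time could produce false support for Hypothesis 2.

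A reader might also infer that leaving out steps/day is an error, since Study Design item 3 calls activity a known confounder of stress. That goes too far: activity may lie on the path from workload to stress. Adjusting for steps/day, splitting factors into between- and within-nurse parts, and a pre-Somni-only analysis are optional additions and not part of this error.

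**What to change.** Replace the equation and the distribution sentence with one linear mixed model per outcome (self-reported stress; mean HRV):

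Y_it = β0 + β1·X_i + β2·F_it + wave_t + u_i + e_it

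where u_i is a participant random intercept, e_it a residual and wave_t a wave or period effect. Then state, before data are seen:

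- **F:** in turn, each sleep, stressful life event, psychiatric and work environment measure or composite. Write F_i instead of F_it where only the baseline value is used.
- **Covariates:** one list for Aim 1, omitting mental health history when F is a psychiatric measure.
- **HRV:** which ring days form the mean matched to each survey. Ring data cover Weeks 1-8 and no HRV before Week 1 is described, so the baseline survey needs an explicit rule.
- **Distribution:** Gaussian, with log HRV if skewed, in place of the count families.

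The cost is mainly SAP wording, slightly more analysis work and a few more model terms. In a pilot of unstated size, that last cost is a reason to keep the covariate list short.

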STUDY DESIGN. This study is a prospective pragmatic pilot trial to generate data needed to inform a fully-powered longitudinal study consisting of nurses across a wider geographic region. There are 4 study components:

1. Electronic Quantitative Surveys (baseline, Week 4 & Week 8) will consist of demographic questions and validated measures for personal characteristics, sleep, stressful life events, psychiatric characteristics, work environment factors, and all psychological health outcomes. (**Table 1**). The surveys will be administered 3 times (baseline, week 4 and week 8) to generate pilot longitudinal data.

2. Psychological Assessment (baseline). To confirm a preexisting psychiatric diagnosis, a *Structured Clinical interview for DSM-5 Diagnosis* (Research version) (SCID-5-RV) will be administered in-person by a Psychiatric Mental Health Nurse Practitioner (PMHNP) at baseline. SCID-5-RV is a semi-structured interview guide for making major DSM-5 diagnoses such as mood disorders, psychotic symptoms, substance use, sleep, and trauma- or stressor-related disorders and takes approximately 45-60 minutes to administer. Studies suggest that prior history of mental illness, such as depression, has been linked to suicide.

3. Physiologic Biomarkers (Weeks 1-8). Heart rate and sleep (hours/day) will be collected using a wearable device, *Oura ring*[®], a piece of jewelry that can be custom fit to each participant. Heart rate variability (HRV), a highly sensitive physiologic metric for stress, is the constant variation in milliseconds between beats, and controlled by the autonomic nervous system. Low HRV is a strong indicator of physiologic stress (fight or flight response) and has been associated with increased risk for suicide attempt. Studies have demonstrated high validity in the assessment of HRV and sleep using the *Oura ring*[®]. The device will also collect activity levels (steps/day) and sleep cycles, known confounders for stress levels.

TABLE 1. Study Variables and Measures

Variable	Operational Definition	Measure
Demographics	Age, Sex, Gender, Race, Ethnicity, marital status, household income, parental status, smoking history, substance use; years of nursing experience	Validated single-items
Sleep	Sleep quality and duration	Pittsburgh Sleep Quality Index ⁴⁴ ($\alpha = .83$) Oura ring [®] Somni [®] 14
Stress	Self-reported stress Heart Rate Variability	Perceived Stress Scale ⁴⁵ ($\alpha = .76$) Oura ring [®]

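### Aim 1 announces linear mixed models for stress and HRV, but the only distributions it names for choosing a link are count families, and neither outcome is a count

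*Combined protocol and SAP*

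**What the plan says.** The Aim 1 paragraph under STATISTICAL ANALYSIS contains three statements that have to be read together.

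- The model class: "We will use linear mixed models to examine the relationships between individual and composite scores of factors", with self-reported stress and HRV as the two outcomes.
- One displayed equation, introduced by "We propose the following model to test all hypotheses". Its left-hand side "represents the outcomes measure (self-report and HRV separately) for each participant". On the right are an intercept, individual covariates and a job or work-environment factor. As extracted, it has no nurse random effect, no time term and no named link.
- The distributional step: "As the primary outcome is stress (mean score and mean HRV") is given as the reason why "possible distributions such as Poisson, zero-truncated Poisson, negative binomial, or zero-truncated negative binomial will be assessed to determine the best fit link function". No selection criterion is stated.

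STUDY DESIGN supplies the rest. Component 3 says that HRV "is the constant variation in milliseconds between beats" and that the ring is worn in Weeks 1–8. Component 1 says of the questionnaires: "The surveys will be administered 3 times (baseline, week 4 and week 8) to generate pilot longitudinal data". The documents do not say whether the stress score is an item mean or a total, or over what period HRV is averaged for each analysis.

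**The concern.** A linear mixed model, in the usual sense, already fixes the distribution (Gaussian) and the link (identity). The last sentence reopens both, and every candidate it names is a model for integer event counts. The reason it gives, that the outcomes are a mean score and a mean HRV, points away from count models. Assessing distributions also does not determine a link, because the two are separate choices.

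This paragraph governs what the plan calls its primary outcome. Two statisticians could fit different models after seeing the data and both claim to have followed it. A Poisson form ties the variance to the mean, so its standard errors depend on the unit or scoring of the outcome. The study describes its own purpose thus: "This study is a prospective pragmatic pilot trial to generate data needed to inform a fully-powered longitudinal study". What is at stake is therefore misleading associations carried into that larger study, not a false confirmatory claim.

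**Working it through.** The plan gives no sample size, power or effect size, so there is no figure to reproduce. From the documents: the four families, the two outcomes, HRV in milliseconds, and a significance level of 0.05 (taken here as two-sided). Every mean and SD below is an assumption.

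**1. Zero truncation.** Truncation matters only if zero has appreciable probability. For a Poisson variable with mean m, P(0) = exp(−m). At m = 40 this is 4.2 × 10⁻¹⁸ and at m = 17 it is 4.1 × 10⁻⁸. The truncated and plain forms are then the same for practical purposes.

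**2. Can fits be compared?** An AIC comparison with a Gaussian needs the count function to behave as a density over continuous values. Integrate exp(−m) m^y / Γ(y+1) over y > 0, and divide by 1 − exp(−m) for the truncated form. A density gives 1.

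| m | Poisson | Zero-truncated Poisson |
|---|---|---|
| 1.0 | 0.834 | 1.319 |
| 1.7 | 0.926 | 1.133 |
| 2.0 | 0.947 | 1.095 |
| 17 | 1.000 | 1.000 |
| 40 | 1.000 | 1.000 |

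The comparison fails on an item-mean scale. It is numerically harmless for HRV in milliseconds or a total score.

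**3. Type I error of a plain Poisson model, one value per nurse, no random effect.** The model takes the variance to equal the mean. Its standard error is therefore wrong by the factor r = SD/√mean, and the actual two-sided error is 2 × (1 − Φ(1.96/r)).

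| Outcome (assumed mean/SD) | r | 1.96/r | Type I error |
|---|---|---|---|
| HRV 40/10 ms | 1.58 | 1.24 | 21.5% |
| HRV 40/15 ms | 2.37 | 0.83 | 40.9% |
| HRV 40/20 ms | 3.16 | 0.62 | 53.5% |
| HRV 40/25 ms | 3.95 | 0.50 | 62.0% |
| Stress total 20/6 | 1.34 | 1.46 | 14.4% |
| Stress total 17/7 | 1.70 | 1.15 | 24.8% |
| Stress total 15/7 | 1.81 | 1.08 | 27.8% |
| Stress item mean 1.5/0.7 | 0.57 | 3.43 | 0.06% |
| Stress item mean 1.7/0.7 | 0.54 | 3.65 | 0.03% |

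As a check by simulation (2,000 runs, gamma-distributed HRV 40/15, one null covariate), the Poisson model rejected in 40% of runs with 50 nurses and 39% with 100. Ordinary linear regression rejected in 4.0% and 4.5%.

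**4. Dependence on scoring.** Divide every total by 10 (10 items assumed). In a log-link Poisson model the slope is unchanged, because only the intercept shifts. The information falls by a factor of 10, so the standard error rises by √10 and the test statistic is multiplied by 1/√10 = 0.316. Any statistic between 1.96 and 1.96 × √10 = 6.20 on the total loses significance as an item mean, on identical answers. In a Gaussian linear model the slope and its standard error both divide by 10, so the test does not change.

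**The case against.** There is a good case on the other side, and much of it stands.

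- **The list is open and linear mixed models are named.** A reader might infer that the plan commits to a count model or rules out a Gaussian one. It does neither. The fault is that the only named candidates are unsuitable.
- **A fit comparison would usually discard Poisson for HRV.** If AIC is the criterion (an assumption, since none is stated), Poisson beat negative binomial in 0 of 300 simulated data sets with overdispersed HRV in milliseconds. The negative binomial type I error was 7.7%, which is little harm. A reader might take 22–62% as the error rate this study will have; it describes one model that the plan does not commit to.
- **The density objection is confined to the item-mean scale.** A reader might infer that every fit comparison in the plan is invalid. The integrals at 17 and 40 show otherwise.
- **The equation may be garbled.** Its left-hand side could be a damaged generalised linear form, g[E(Y)]. The link sentence would then belong to it, and the clash with linear mixed models would be partly loose terminology. The missing random effect and time term should be read with the same caution.
- **Repeated HRV values are not established.** Surveys occur three times, but no HRV average per survey is defined. With one mean per nurse, a random intercept could not be separated from residual error.

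None of this makes count families suitable for a mean score or a quantity in milliseconds, or makes the choice of a distribution the choice of a link.

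**Conclusion.** The point holds as a defect in a stated analysis rule for the primary outcome. All four named families are for counts, neither outcome is a count, zero truncation has no purpose for HRV, and family and link are merged.

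The size of the harm is conditional. It is small if a negative binomial model is used for HRV in milliseconds or for a total score. If a plain Poisson model is used on one value per nurse, the error can go either way: about 22–62% for HRV under the assumed mean of 40 ms and SD of 10–25, and below 0.1% for an item mean. On an item-mean scale the count AICs are also not comparable with a Gaussian's, and Poisson conclusions depend on the scoring. The documents supply none of the means, SDs or sample sizes needed to say which case would arise. In a pilot this warrants a correction to the wording; it does not show that the results will be wrong.

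**What to change.** Delete the count and zero-truncated candidates and the link-function wording from Aim 1. In their place, state that:

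- self-reported stress (total or item mean, to be specified) and mean HRV (averaging window for each analysis point, to be specified) will each be analysed with a Gaussian linear model with identity link;
- where there are repeated values per nurse, the model includes a nurse random intercept and time as a fixed effect, and the displayed equation shows both;
- if HRV is a single mean per nurse, ordinary linear regression is used;
- one continuous-outcome fallback for skewed HRV, for example log HRV, is named in advance.

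A numerical skewness trigger, cluster-robust standard errors as a sensitivity analysis, and an explicit bar on other families are optional.

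The cost is SAP wording, with no new data. A Gaussian model may fit less well under strong skew or floor and ceiling effects. If the log HRV fallback is used, its effects are read as ratios and not as differences in milliseconds.
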